Screening Visit: Patients will complete a medical history review during their screening visit to determine subject eligibility. As outlined by the University of Michigan clinical care guidelines, subjects will complete a Covid-19 test prior to the stress test. A results will be provided to the study team. Patients will complete an exercise stress test as part of the screening procedures. The %HR the stress test will start with will be the patient's resting heart rate, typically below 100. The %HR max will vary per patient. This is calculated by 220-age. It is possible that this value will not be met but it is also possible that the predicted %max HR will be exceed. The Cornell protocol will be utilized for this study. The stress test will be performed on a treadmill. Only patients that have a normal exercise stress test will be allowed to participate in this study. To mitigate the risks associated with the exercise stress test, the test will be overseen by medical professionals that are ACLS certified including a physician, nurse and/or exercise physiologist. Patients with an abnormal EKG will be referred to their primary care physician and not cleared for participation

Justification of the target population: We are focusing on an obese population because we have built a collaborative obesity-DSP team with 5 years of experience recruiting and studying this population. Focusing on an obese population, rather than a diabetic population, increases the number of people affected by our results. Furthermore, our observational data revealing a high prevalence of DSP in obese participants without diabetes highlights that DSP is an important issue for all obese patients. Limiting recruitment to the U-M's bariatric surgery clinic allows us to evaluate the effect of both HIIT and bariatric surgery on DSP outcomes. Selection bias will be reduced by requiring that patients have started the bariatric surgery process by seeing a physician assistant or bariatric surgeon. Patients will also be referred to a dietician. The limited generalizability to other populations can be addressed in subsequent studies.

C3.2. Interventions:

C3.2.1 HIIT: Training sessions during the 24-mo will be supervised by exercise physiologists and trainers. [name], the director of the Human Phenotyping Core (HPC) of the U-M's Nutrition and Obesity Research Center will provide oversight of this aspect of the study given his vast expertise on the impact of HIIT and other exercise interventions on metabolic outcomes.⁴⁶⁻⁵⁰ The exercise modality will be self-selected (e.g., walk/run (outdoors or treadmill), elliptical machine, stair climbing, cycling), and subjects will be encouraged to regularly vary the exercise modality to reduce risk of overuse injury and to enhance the variety of the exercise program.

Subjects receiving the surgery intervention will start the HIIT regimen no sooner than 4 wk post-operatively to provide an adequate time to heal from the procedure. All subjects will first undergo a familiarization program for 1 week where they all will perform conventional exercise (steady-state at 65% HR max for 25 min/session). After this 1-week familiarization period, subjects will begin the HIIT regimen. The first session of the "ramp-up" period will entail 19 min of conventional exercise at 65% HR max, followed immediately by 2 x 1 min intervals at 90% HR max with a 1 min active recovery period between intervals at 50% HR max, and a 3 min cool down at 60% HR max after the second interval. After that first ramp up training session, 1 additional high intensity interval will be added to each training session, so by the beginning of week 3 of HIIT training, subjects will reach the full HIIT training protocol of a total of 10 x 1 min intervals at 90% HR max (**Figure 2**). They will continue this training protocol, 3 sessions/wk (2 supervised and 1 unsupervised), for 24-mo. Subjects who may feel challenged by the rate of increase in the number of intervals during this ramp up period will be allowed to increase the number of intervals at a slower pace, but all subjects must reach the full HIIT protocol during week 4 of HIIT training. Of note, our team regularly has patients with obesity and/or diabetes progress to the full protocol HIIT within 3 weeks, demonstrating the feasibility of this training approach in our population. 38, 41, 62, 63

Participant safety and well-being during the exercise interventions: Caution is warranted when initiating an exercise training study in sedentary obese adults, and additional concern is needed when participants are required to exercise at high intensity. We take this issue seriously and extreme caution will be taken throughout the project to greatly reduce risk associated with the exercise regimen. Patients will be provided medical oversight and any injuries, and/or medical concerns that may arise in our patients during the course of this project will be address by [name], the co-investigators, the patient's Bariatric Surgery Team, and the patient's primary care physician. It is important to note, however, that several studies have now been published demonstrating that the HIIT protocol in this project can be used safely in patients with obesity, cardiovascular disease, and type 2 diabetes.⁶⁴⁻⁶⁶ Furthermore, another study demonstrated the safety of exercise interventions in those with DSP from type 2 diabetes with no serious or unanticipated adverse events reported.⁶⁷ Notably, all patients will complete an exercise stress test and exercise will be supervised for the full 24 mo of the HIIT intervention.

Exercise compliance: In addition to the 2 supervised sessions per week, subjects will be asked to complete 1 unsupervised session. To improve compliance in both types of sessions, patients will receive monthly phone calls from research staff to discuss potential solutions to barriers. Subjects will be provided with a wearable physical activity monitor with a visible heart rate display. Importantly, the data from these devices are downloaded wirelessly to a computer and/or mobile device, which then automatically updates their physical activity profile on their personal web-page. Our research study coordinator will receive permission to access each subject's physical activity profile, enabling us to assess their compliance remotely. The data reported on the website includes a 24-hr profile of heart rate and calories expended, allowing us to clearly distinguish compliance to the HIIT regimen. We will assess each subjects' physical activity profile on a weekly basis and record how many prescribed exercise sessions were successfully completed. If participants do not have access to the appropriate technology, we will make alternative arrangements such as providing them with an inexpensive mobile device with the necessary technology, providing a recordable heart rate monitor to wear during exercise, or collecting training logs.

- C3.2.2 Routine exercise counseling: Patients receive counseling regarding exercise as a routine part of their participation in the bariatric surgery clinic. Specifically, they are counseled to participate in 60 min of aerobic exercise daily in addition to 2-3 non-consecutive days of strength training workouts every wk. Patients are encouraged to contact the bariatric conditioning program, obtain a gym membership, purchase exercise equipment, join a walking group, and/or sign up for fitness classes (employer or city parks and recreation).
- C3.2.3 Bariatric surgery: Patients will undergo the surgical procedure as recommended by their surgeon as part of their routine care at a bariatric clinic. Our preliminary data indicates that 85% of patients had a sleeve gastrectomy, 15% had a Rou-en-Y gastric bypass at the University of Michigan, and none had an adjustable gastric band. We expect a similar distribution of procedures as part of this proposed study. Patients undergoing sleeve gastrectomy and Roux-en-Y gastric bypass have similar weight loss and time to stabilization, which limits potential confounding by type of surgical procedure. ^{59, 60} Specifically, weight loss is typically 60-80 pounds at 6 mo, and 100-120 pounds at one year with stabilization at 1-1.5 yr. In contrast, adjustable gastric band procedures result in a 45-55 pound weight loss at 6 mo with stabilization at 2 yr, but this procedure is not performed at U-M. Of note, as part of their routine post-operative care, patients are supplemented with a multivitamin, sublingual B12, and calcium. Furthermore, patients have laboratory monitoring including comprehensive metabolic panel, complete blood count, B12, TSH, ferritin, and vitamin D. The prophylactic supplementation and laboratory monitoring mitigate the potential for nutritional deficiencies to lead to nerve injury and subsequent DSP. The strength of this approach is that it mirrors current practice in the bariatric surgery, a specific nutritional deficiency other than B12 deficiency is often not found. ⁶⁸
- **C3.3. Metabolic phenotyping:** These tests will aid in the appropriate description of the population, allow for adjustment of potential confounding as needed, and may provide further data in support of the metabolic factors that improve when IENFD increases over time.

Phenotypic tests will occur at baseline, 3, 12, and 24 mo, with the exception of the GTT which will only be performed at baseline. The metabolic phenotyping tests include:

 2 hr, 75 gram oral GTT with glucose and insulin levels drawn at 0, 30, 60, 90, and 120 min to allow categorization of glycemic status as well as calculation of Oral Glucose Insulin Sensitivity (OGIS).
Participants with a known diagnosis of diabetes will not complete an OGTT. Participants with a fasting glucose >126 mg/dL will not complete the test. Fasting glucose and insulin levels will be drawn at the 3, 12 and 24 month time points;

- 2. Hemoglobin A1C;

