Aim 2: Explore the impact of surgical weight loss on DSP outcomes (non-randomized). We hypothesize that bariatric surgery patients will have better DSP outcomes compared to patients without surgery, but the effect will be less than the effect of HIIT. To test this hypothesis, we will stratify the HIIT randomization in Aim 1 1:1 for those that have and those that do not have surgery. This will allow us to explore the effect of surgical weight loss on DSP outcomes without requiring an expensive, randomized, surgical intervention trial. Linear mixed models will determine the longitudinal effect of surgical weight loss on DSP. We will also assess the interaction between HIIT and surgical weight loss to evaluate the combined effect of these two interventions.

Impact: We will determine whether HIIT and/or surgical weight loss are promising disease modifying treatments for DSP. If successful, our phase 2 trial will form the basis of a large, pivotal phase 3 trial of exercise and/or weight loss for the treatment of DSP. Either would be the first disease modifying therapy for this common, highly morbid condition.

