The proposed trial is *highly innovative* and represents a paradigm shift in current treatment strategies for the prevention and treatment of DSP for patients with and without diabetes. We strongly contend that the diabetes research community must move beyond glucose control alone to more comprehensive treatment approaches for diabetic complications. Moreover, a successful trial would bring us one step closer to a desperately needed intervention for patients without diabetes, including the large obese population, to prevent and improve DSP. The *innovation* in this proposal is high and includes: 1) an exercise regimen (HIIT) that is time efficient, yields improved metabolic health even after short term participation, and is better tolerated with higher compliance in an obese population than conventional exercise; 2) a study design that allows comparisons between exercise, bariatric surgery, and the combination of these interventions without the need for an expensive, randomized surgical intervention phase 2 trial; 3) a main outcome measure (IENFD), which allows sensitive and objective

quantification of nerve fiber loss and regeneration over time, with true potential to capture early changes of DSP; 4) comprehensive patient-oriented outcomes, including multiple measures of DSP-related pain, daily function, and DSP-specific quality of life outcomes; 5) the use of a non-invasive measure of DSP, corneal confocal microscopy (CCM), to compare with the primary outcome of this trial, IENFD, to inform future clinical trials (see C.3.4.2); and 6) an analysis plan that investigates the potential modifying effects of sex on DSP outcomes, the differential effect of sleeve gastrectomy versus Rou-en-Y gastric bypass on DSP outcomes, and the weight loss independent effects of bariatric surgery by incorporating early outcome measures.

C. Approach

The clinical trial design summary for Aims 1 and 2 is shown in Figure 1. All patients will be recruited from a **Bariatric Surgery** Clinic, including those that do and those that do not have surgery. We will randomize patients 1:1 to either the HIIT exercise regimen or routine exercise counseling. Randomization will be stratified 1:1 for

those that do and

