those that do not have surgery. We will also stratify by glycemic status to limit confounding. Randomization will be performed using permuted blocks, with a block size known only to the statistician. We will perform longitudinal analyses using linear mixed models to study the evolution of IENFD from baseline to 2 yr (4 measures in total). We will compare the effect of HIIT, bariatric surgery, and the combination of HIIT and surgery on all outcomes.

C1. Aim 1: Examine the efficacy of a HIIT exercise regimen on DSP outcomes (randomized)

C1.1. Introduction: There is an urgent need for a disease modifying therapy for the prevention and treatment of DSP. Currently, physicians only have neuropathic pain medications and glucose control to offer patients with DSP.^{7, 27} However, glucose control alone is not effective at preventing DSP and many patients with diabetes develop DSP despite good glucose control.²⁷ Similarly, no disease modifying interventions exist for the increasing population with pre-diabetes and/or obesity. Thus, it is essential to identify new interventions that can prevent and treat DSP. To date, uncontrolled studies support improvement in the natural history of DSP decline over time after an exercise intervention.²⁸⁻³⁰ The next step is to determine whether a randomized, intensive, exercise intervention improves DSP outcomes compared to routine exercise counseling.

C1.2. Justification & feasibility:

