| Anthropometric measures^ | | X | X | X | X |
| Orthostatic Hypotension Assessment [^] | | Х | X | X | Х |
| Quality of Life measures: | | | | | |
| NeuroQol | | X | X | X | X |
| Questionnaires | | X | Х | Х | X |
| Demographics | | X | | | |
| Functional Assessments | | | , . | , . | |
| Berg Balance Scale [^] | | X | X | X | X |
| 8-foot Get Up and Go Test^ | | X | X | X | X |
| Modified Falls Efficacy Scale | | Х | X | Х | Х |
| Aerobic Assessment | | | | | |
| VO2 max | X | | | | X ⁺ |
| | | | | | |
| Dual Energy X-ray Absorptiometry | | | | | |
| Duai Lineigy A-iay Absorptionietry | | X | | | X |

^{*}Randomization to exercise protocol to occur after baseline visit

Data collected for clinical purposes as part of the Adult Bariatric Surgery Program will be reviewed as part of this study and included in the study records.

- **C3.6. Timeline and milestones:** The planned study duration is 5 yr, with 2 yr of subject accrual, 2 yr of subject follow-up, plus 1 yr for analysis and results presentation.
- **C3.7. Statistical analysis:** The four treatment groups (HIIT/no surgery, HIIT/surgery, routine exercise/no surgery, routine exercise/surgery) will be compared with respect to demographic and baseline variables (e.g., age, sex, glycemic status, OGIS, BMI, etc.). If a significant difference is found in any variable, the models described below will be fitted after adjusting for these variables.
- C3.7.1 Analysis of primary outcome: The primary outcome is IENFD at the proximal thigh, measured at baseline, 3, 12, and 24 mo. Exploratory analysis will be performed to assess the need for any transformation

^{*}Only participants randomized to the HIIT will complete a second time

 $^{^{\}mathsf{T}}$ Participants can consent to have skin biopsy added to biorepository

[^]Participants may complete the consent and outcomes virtually prior to the upcoming visit to decrease in-person interaction due to Covid-19. If the outcome cannot be completed successfully it with be completed during the visit.

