where β_{00} is the population-averaged intercept, Z_i is the matrix of main effects and interaction corresponding to HIIT exercise and bariatric surgery, \underline{X}_{it} is the matrix of fixed covariates (demographic and baseline characteristics), λ and θ are the vectors of corresponding fixed effects parameters, β_{0i} is the subject-specific random (intercept) effect capturing heterogeneity across subjects due to unmeasured confounders, and en is the random error characterizing variation due to sources like within-subject fluctuations and measurement error. The random effect β_{0i} is assumed to follow a normal distribution with mean zero and variance σ^2_{sub} , and the eit's are assumed to be distributed normally with mean **0** and variance covariance matrix R (non-diagonal). Furthermore, we also assume that θ_{0i} and e_{it} are independent. Maximum likelihood method will be used to estimate the model parameters. We will use Akaike Information Criterion (AIC) and Schwarz Bayesian Information Criterion (BIC) to guide the selection of the covariance structure. Inference for λ (which is of primary interest) will be based on Wald tests. We will use PROC MIXED in SAS to fit the above model. To explore potential non-linear or threshold effect of treatment exposure on IENFD we will use a nonparametric regression model fitted using the framework of generalized additive models (GAM). 115 Given the exploratory nature of the research proposed here, the GAM models will allow us the flexibility to include a smooth functional term instead of restricting to a linear relationship. The smoothing term is fitted by using penalized regression splines or locally smoothed loess curves, with the degree of smoothness chosen in a data-adaptive way, using cross-validation techniques. We will use the gam function in the mgcv package available in the R software to fit these non-parametric regression models. We will perform sensitivity analyses to assess how subjects who withdrew affect conclusions of the analysis. An intent-to-treat analysis set (including subjects who are randomized, treated, and have a baseline IENFD) will be used to assess treatment effects, with multiple imputation methods¹¹⁶ employed to impute outcomes for subjects with missing post-baseline data. Depending on the extent and pattern of missingness, other simpler sensitivity analyses may be used: e.g., subjects completing the study (completers) may be analyzed using a repeated measures analysis of variance model. The model will include the same covariates that are included in the primary analysis.

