- **C3.10. Recruitment and retention plan:** [name] has experience recruiting obese participants for two epidemiologic cohorts, his NIH K23 and 2P30-DK020572 grants, that provided the preliminary data for the proposed study. He works closely with [name] (project coordinator) and [name] (research coordinator) on these projects. Both coordinators have successfully recruited subjects for these studies, developed strategies for retention, and can perform the outcomes measures required for this proposal.
- C3.10.1 Recruitment strategies: Patients will be recruited from a bariatric surgery clinic. Recruitment for the study begins at the informational session, where flyers are passed out providing information about the study as well as contact information for the study team. Patients are then recruited one-on-one during their bariatric surgery clinic visits. Patients meet individually with the study coordinator to discuss the study, answer questions, and begin the scheduling process. Patients are then followed as they complete the requirements prior to surgery, and are emailed at different time points to check for interest in participation. The final face-to face interaction for recruitment is during the required nutrition information session. Patients will be consented once they have made a decision whether or not to have surgery. This multi-step approach to recruitment has been effective for our ongoing bariatric surgery study. Compared with the start of the ongoing project, we have added multiple points of face-to-face contact and added a mixed media presentation, which will only increase the feasibility of the current proposal.
- C3.10.2 Retention strategies: Patients will be emailed and/or called to schedule their 3, 12, and 24 mo visits approximately 2-3 mo prior to the date. We will also call patients monthly to address any concerns and discuss compliance. This limits the amount of time that the study team is not in contact with the participant, helping to increase patient retention. Patients are mailed out a reminder post-card just prior to the 1-yr and 2-yr mark, thanking them for their participation and reminding them that we will be in contact with them. This patient population has proven to be committed and motivated to participate in our current study, with 94% retention.

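### Glycemic strata balance the HIIT arms but not surgery versus no surgery, and the analysis names glycemic status only under a significance trigger that conflicts with the model section

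*Protocol*

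**What the plan says.** **Allocation.** The Protocol's C. Approach randomises exercise only: "We will randomize patients 1:1 to either the HIIT exercise regimen or routine exercise counseling". The strata are surgery status and glycemic status, the latter with the reason "We will also stratify by glycemic status to limit confounding". The sentence does not say which comparison it has in mind.

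**Surgery.** Section 2 describes the second aim as "Aim 2: Explore the impact of surgical weight loss on DSP outcomes (non-randomized"). C3.10.1 places the choice ahead of enrolment: "Patients will be consented once they have made a decision whether or not to have surgery". C3.1 fixes 35 patients in each of the four groups and sets no glycemic quota or matching.

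**Analysis.** Four places bear on adjustment:

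- C3.7: the four groups "will be compared with respect to demographic and baseline variables (e.g., age, sex, glycemic status, OGIS, BMI, etc".). It continues: "If a significant difference is found in any variable, the models described below will be fitted after adjusting for these variables".
- C3.7.1, opening paragraph: covariates of demographic, clinical and baseline type will be adjusted for. No condition is attached and none is named.
- C3.7.1, model definition: the covariate term "is the matrix of fixed covariates (demographic and baseline characteristics"), again not itemised.
- C3.3: metabolic data allow confounding to be adjusted for if needed.

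**The concern.** Stratified randomisation balances a factor between the arms that are randomised, and only those. Here these are HIIT and counselling. In that comparison glycemic status is not a confounder in expectation, and stratification removes chance imbalance. In the surgery comparison it can be a true confounder. The protocol treats it as prognostic (A2 gives odds ratios for DSP of 4.90 for diabetes and 3.82 for pre-diabetes), and patients who choose surgery may differ in glycemic mix from those who do not.

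The surgery contrast therefore depends on the model. If the C3.7 rule governs, a stratification factor and likely confounder enters only when a baseline test reaches significance. That test asks whether a difference is detectable with about 35 patients per group, not whether it is large enough to bias the estimate. If C3.7.1 governs, adjustment is unconditional but its content is open. At stake are Aim 2 and the comparison of HIIT with surgery, which could carry a difference in glycemic mix as if it were an effect of surgery. For Aim 1 the stake is a modest loss of precision.

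**Working it through.** The protocol gives no figure for this confounding. Its power statement (C3.8) plays no part in the point, but it does hold as an inequality: with 30 per group and a standardized effect of 0.9, 0.9 × √(30/2) − 1.96 = 1.53, or about 94% power, against at least 80% stated.

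**1. What stratification achieves.** Inputs: 140 patients, 70 with and 70 without surgery (C3.1); HIIT allocated 1:1 in permuted blocks within surgery-by-glycemic strata (block size 4 assumed). Over 2,000 simulated trials, the difference in diabetes share between HIIT arms had mean 0 and SD 0.015, against about 0.08 without stratification. The surgery-minus-no-surgery difference stayed at whatever the two source mixes implied.

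**2. Bias in the surgery contrast if glycemic status is left out.** The surgery mix is taken from the bariatric cohort in Table 3: 28.2% normal, 36.6% pre-diabetes, 35.2% diabetes. The no-surgery mix is assumed. Let diabetes lower IENFD by D fibers/mm relative to normoglycemia, and pre-diabetes by D/2 (assumed; D = 1, 2, 3).

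Bias = −D × [difference in diabetes share + ½ × difference in pre-diabetes share]

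| Assumed no-surgery mix (normal/pre-diabetes/diabetes) | Bracket | Bias at D = 1, 2, 3 |
|---|---|---|
| 40/36/24% (weight-management cohort, Table 3) | 0.112 + ½ × 0.006 = 0.115 | −0.12, −0.23, −0.35 |
| 20/30/50% | −0.148 + ½ × 0.066 = −0.115 | +0.12, +0.23, +0.35 |

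The simulations agreed within Monte Carlo error (SE about 0.02). With glycemic status in the model the simulated bias was about −0.01, that is, zero within error.

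**3. An extreme scenario.** C3.8 cites a fall from 19 to 13 over 26.7 months, so 6 × 24/26.7 = 5.39 over 24 months. Suppose every dysglycemic patient declines by 5.39 and every normoglycemic patient by 0. A 10-point gap in dysglycemia then shifts the contrast by 0.10 × 5.39 = 0.54, and a 20-point gap by 0.20 × 5.39 = 1.08. The latter is 34% of the planned surgery difference, 0.2 − (−3) = 3.2.

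**4. How often the C3.7 trigger fires.** Chi-square test at p < 0.05, same setting:

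| True glycemic mix, no surgery | Across four groups | Surgery vs no surgery |
|---|---|---|
| Same as surgery | 0.3% | about 5% |
| 40/36/24% (11-point diabetes gap) | about 5% | about 31–33% |
| 20/30/50% | about 5% | about 33% |
| 48.2/26.6/25.2% (20-point dysglycemia gap) | about 18% | about 59% |

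The four-group test has six degrees of freedom. Four of them concern HIIT versus counselling within surgery strata, where stratification forces near-balance. The first row shows the consequence: under no difference the test rejects in 0.3% of trials instead of 5%.

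**5. HIIT precision if the stratum is omitted.** If glycemic status explains a share R² of outcome variance (assumed 5%, 10%, 15%), the standard error is inflated by 1/√(1 − R²) = 1.026, 1.054, 1.085. The true size of a nominal 5% test is 2 × [1 − Φ(1.96/√(1 − R²))] = 4.4%, 3.9%, 3.4%.

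**The case against.** The strongest reply has four parts.

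- *The stratification sentence makes no claim about surgery.* This stands. The sentence follows the description of the HIIT randomisation, and Aim 2 is openly labelled non-randomised and exploratory. A reader might infer that the protocol offers glycemic strata as protection for the surgery comparison, because the same text goes on to promise comparisons of HIIT, surgery and the combination; but the text does not say so. For HIIT the benefit is real, and calling chance imbalance confounding is loose wording.
- *Adjustment is promised.* This stands in part. A reader might infer that glycemic status will be left out of the model. C3.7.1 does not support that: its unconditional adjustment for unnamed clinical and baseline characteristics could include it. What remains is that C3.7, the one place that names the variable, makes it conditional.
- *Listing covariates belongs in a SAP.* True, and a SAP that is not at hand may do it. But a significance trigger written into the protocol, at odds with the next subsection, is a stated rule and not an omission.
- *The larger bias figures are not supported.* This stands. The 6-fiber decline comes from patients with both pre-diabetes and DSP, whereas DSP prevalence in the bariatric cohort is 7.7% in pre-diabetes and 28.0% in diabetes (Table 4). It is also a decline without intervention, and half of each surgery stratum is assigned to HIIT.

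**Conclusion.** The point holds in limited form. By design, glycemic strata protect the HIIT comparison and cannot balance surgery against no surgery; this needs no numerical assumption. The adjustment rules in C3.7 and C3.7.1 do not agree, and the conditional one would usually miss a glycemic difference of the size considered here (about 5% to 18% detection).

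The sizes are illustrative. A bias of about 0.1 to 0.35 fibers/mm, of either sign, rests on assumed no-surgery mixes and assumed IENFD differences by glycemic status. About 1 fiber/mm needs the extreme scenario and should not be read as an expected value. The 3% to 8% inflation of the HIIT standard error applies only if the term is omitted and R² is 5% to 15%; it makes the HIIT test slightly conservative and does not raise the false-positive rate. Adjusting for glycemic status removes only its own part of the confounding of surgery; other reasons for choosing surgery remain.

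**What to change.** 1. In C3.7.1, make glycemic status (normal, pre-diabetes, diabetes) a fixed three-level term in every HIIT and surgery model, whatever the baseline comparison shows.
2. In C3.7, remove the significance trigger for glycemic status so that the two sections agree. The four-group baseline table can stay as description.
3. In C. Approach, say that stratifying by glycemic status limits chance imbalance between the HIIT arms, and that confounding of the surgery comparison is handled by adjustment, which covers only the measured factors in the model.

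Cost: two degrees of freedom and a few sentences. Glycemic status is categorised at baseline and is needed for the stratified randomisation, so no new data are required. Letting its effect vary by visit is optional and costs more: 2 + 2 × 3 = 8 parameters with four visits, or 2 + 2 × 2 = 6 if only the three post-baseline visits are modelled.
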